## **11.0 ATTENTION TO HEALTH EQUITY**

When examining the adoption and implementation of EIMG, we will pay particular attention to questions of health equity across all dimensions of RE-AIM, including:

1. **ADOPTION:** We will examine the ability of lower resource clinics to adopt EIMG to the same extent as high resource clinics; necessary adaptations to EIMG at lower resource clinics for more equitable adoption of EIMG; and adapting clinic context to better support staff efforts to utilize EIMG with their patients.
2. **IMPLEMENTATION:** We will examine characteristics of providers implementing EIMG with a high vs low proportion of patients; differences in clinics and staff capacity; resources to deliver EIMG on an ongoing basis; EIMG implementation strategies distribution among various clinic staff; the impact of setting characteristics on successful EIMG implementation.
3. **REACH –** We will examine the representativeness of patients reached (i.e., across race/ethnicity, education) compared to all eligible patients; equitableness of the reach of EIMG; which population subgroups are not being equitably reached; barriers to participation in the community-based PA programs.
4. **EFFECTIVENESS –** We will examine whether the health benefits of EIMG are experienced equitably across subgroups based on social dimensions and social determinants of health; certain subgroups experience higher levels of barriers, negative effects, or burden due to EIMG participation.
5. **COST –** Participation may present considerable burden to patients, resulting in unintentional inequities. We will examine patient participation in the PA program, paying consideration to cost, time, resources, and unintended social consequences, discussing findings with the EIMG Advisory Board to develop more equitable and sustainable outcomes.

## 12.0 STATISTICAL ANALYSES

### 12.1 Primary Outcome

To determine differences in implementation (i.e., delivery fidelity) and reach (i.e., number, proportion, and representativeness of patients) before and after EIMG integration at Prisma Health clinics.

### 12.2 Statistical Methods for Primary Analysis

Clinic level nominal characteristics will be summarized as count and proportion; quantitative characteristics (e.g., patient census, provider census, etc) will be summarized as using the median and interquartile range. Patient level data will be summarized monthly by clinic using count and proportions for categorical data and mean (standard deviation) or median (interquartile range) as appropriate.

Clinic level characteristics will be compared between adopting and non-adopting clinics to look for indicators that may be leveraged to improve the adoption of EIMG into the patient care workflow. Similarly, there may be providers within participating clinics that choose not to adopt EIMG (refer eligible patients to the physical activity program); characteristics of the providers will be compared to look for ways to adopt / improve EIMG referral.

The primary endpoint will be analyzed on an intent-to-treat basis. This means that clinics will be analyzed according to their agreement to adopt regardless of their subsequent participation. For analyses at the patient level, patients within EIMG-adopting clinics that receive referrals will be analyzed as EIMG participants regardless of their subsequent actions / participation. Referred patients will be considered as part of the “EIMG group” even though they may not be perfectly compliant or follow the prescribed dose of exercise in the physical activity program.

The effect of EIMG on outcomes for overall reach will be analyzed using generalized linear mixed models (GLMM). The use of the GLMM accounts for the variability between clinics (random intercept) and the random effect of time within each clinic. The right-hand side of the model will have the same form. The left-hand side of the model may require the use of different link functions. Our experimental units are the clinics themselves with the observational units being the EIMG eligible patients nested within each clinic. The analytical models will have the following form:

$$g(Y_{ijk}) = (\beta_0 + \mu_{0i}) + \beta_1 EIMG_j + (\beta_2 + \mu_{2i})X_i + (\beta_3 + \mu_{3k})T_k + (\beta_4 + \mu_{4ijk})EIMG_j T_k + e_{ijk}$$

[figure not shown]
The subscripts i, j and k refer to clinic, EIMG status and time (monthly), respectively.  $Y_{ijk}$  is the clinic level outcome measure;  $g(Y_{ijk})$  is the link function;  $\beta_0$  is the mean response across clinics;  $\beta_1$  is the effect of EIMG;  $\beta_2$  is the mean effect of clinic level covariates controlling for EIMG status;  $\beta_3$  is the effect of time;  $\beta_4$  is the effect of the interaction between EIMG status and time. The remaining terms in the model represent random variability and are assumed to have an expected value of 0 and associated non-zero variance. Specifically,  $\mu_{0i}$  is the uncertainty term for the intercepts between clusters;  $\mu_{2i}$  is the uncertainty term for clinic level covariate slopes between clusters;  $\mu_{3k}$  is the uncertainty term for the effect of time;  $\mu_{4ijk}$  is the uncertainty term for EIMG by time interaction between clusters; and  $e_{ijk}$  is the unexplained residual.

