### 12.6 Poolability of Data

We intend to perform the primary treatment effect analysis by pooling data from all clinics. It is possible that treatment effect will differ across clinics and this will be investigated. We will fit a model with site by treatment interaction and if significant (at 0.05 level), we will present treatment effects by clinic. Although the study is not powered for detection of different treatment effects across clinics, this analysis will provide insight into possible varied treatment effects across sites or reassure that data can reasonably be pooled over sites with respect to the treatment effect.

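### The primary model's equation contradicts its own description of the random effects, and the training effect has no clinic-level random term

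*Combined protocol and SAP*

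**What the plan says.** All of this is in section 12.2 of the combined protocol and SAP, except where noted.

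- In words, the model "accounts for the variability between clinics (random intercept) and the random effect of time within each clinic". Clinics are named as the experimental units.
- Indices: "The subscripts i, j and k refer to clinic, EIMG status and time (monthly), respectively". The response "is the clinic level outcome measure", and section 12.3 counts eight observations per clinic, four under each training level.
- In the equation, the intercept has the random term μ0i. The training effect β1 has none. The clinic covariate X_i has μ2i, time has μ3k, and the training-by-time product has μ4ijk.
- Definitions: μ3k "is the uncertainty term for the effect of time", with no mention of clinic. μ4ijk "is the uncertainty term for EIMG by time interaction between clusters". μ2i "is the uncertainty term for clinic level covariate slopes between clusters".
- Section 12.6 plans a separate model with a site-by-treatment interaction and says: "It is possible that treatment effect will differ across clinics and this will be investigated".

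**The concern.** A programmer cannot code this model without choosing between the prose and the equation, and the choice changes the primary test. All clinics enter in one wave (section 8.1) and training falls in the first half of month 5 (section 8.4), so training status is practically a function of calendar month. If μ3k is fitted literally, the step becomes a contrast among eight months. If the prose is followed, it becomes a contrast replicated across clinics. These have different standard errors and degrees of freedom.

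Under either reading, nothing lets the size of the training step differ from clinic to clinic. If clinics do respond differently, the standard error of the average step omits part of the uncertainty that comes from having only 10 to 20 clinics.

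**Working it through.** **1. What each random term implies.** Covariances for unit-variance random terms, with months 1 to 8 and training from month 5:

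| Term | Same clinic, months 6 and 8 | Different clinics, month 6 |
|---|---|---|
| μ3k·T (equation) | 0 | 6 × 6 = 36 |
| μ3i·T (prose) | 6 × 8 = 48 | 0 |
| μ4ijk·EIMG·T (equation) | 0 | 0 |
| μ1i·EIMG (clinic training step, absent) | 1 | 0 |

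The time term as written links clinics within a month and links nothing within a clinic, the reverse of the prose. μ4ijk only adds variance to post-training observations and carries no persistent clinic difference. If patients were the rows, as 12.2 also suggests, it would be a clinic-by-month term, still not a clinic-specific training effect.

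**2. The plan's own power figure.** Inputs from 12.3: clinic SD 0.01, residual SD 0.01, significance level 0.05 (taken as two-sided), 10 clinics, and power reported as the minimum of 100 batches of 100 simulations. The monthly profile was 0.001, 0.004, 0.007, 0.010, 0.030, 0.033, 0.036, 0.039. The 0.02 jump is read as including one month of trend, so the step coefficient is 0.017. With a random intercept only and an identity link, average power is 95% and the minimum batch 91%, against 92% stated. If the jump is instead 0.02 beyond the trend, these are 99% and 96%. The stated figure is thus matched closely without any clinic-specific time or training variation. The interaction figures (40% and 78%) did not both reproduce under one reading and are not used here.

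**3. Type I error if the clinic training step is left out.** Assumptions: identity link, random-intercept model, linear time trend, clinic step SD τ. The documents give no τ.

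- Information on the step per clinic, adjusted for time: 2 − 8²/42 = 0.476.
- True variance of the average step: (0.0001/0.476 + τ²)/n = (0.00021 + τ²)/n.
- Variance the model reports, on average: [0.0001 + 2τ²(n−1)/(7n−2)]/(0.476n).

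For n = 10 and τ = 0.01, the true SE is √(0.00031/10) = 0.00557. The reported SE is √(0.00012647/4.76) = 0.00515, a ratio of 0.926. With critical value 1.995 on 68 df, the rejection rate is about P(|t| > 1.995 × 0.926) = 6.9%. Simulation (20,000 null trials per cell) agrees:

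| τ | 10 clinics: formula / simulated | 20 clinics: formula / simulated | Clinic-level t-test, simulated |
|---|---|---|---|
| 0 | 5.0% / 4.8% | 5.0% / 5.3% | 5.0–5.2% |
| 0.005 | 5.6% / 5.7% | 5.5% / 5.4% | 4.8–5.2% |
| 0.01 | 6.9% / 7.1% | 6.8% / 7.1% | 4.9–5.2% |
| 0.02 | 9.8% / 10.1% | 9.5% / 9.8% | 4.8–4.9% |

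If clinics differ only in time slope (assumed SD 0.003 per month), the error goes the other way. The true variance stays 0.00021/n, but for n = 10 the residual variance is estimated at 0.0001 + 42 × 0.003² × 9/68 = 0.00015. The SE ratio is 1.22 and the rejection rate about 1.7% (simulated about 2%).

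**4. Power once clinic-specific steps and slopes are allowed for** (t-test on n−1 df, step 0.017, average power):

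| τ | 10 clinics | 20 clinics |
|---|---|---|
| 0 | 91% | 99.9% |
| 0.005 | 88% | 99.7% |
| 0.01 | 77% | 98% |
| 0.02 | 49% | 83% |

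**The case against.** **The intent is visible.** The prose says time varies within clinic and that the interaction varies between clusters, so μ3i and μ4i may have been meant. This is plausible and removes part of the problem. A check of that reading (10 clinics, 3,000 null trials) rejected in 4.8% on residual df with slope SD 0.003, so the 2% figure disappears. With step SD 0.01 it rejected in 7.7% on residual df and 4.8% on n−1 df. With step SD 0.02 it still rejected in about 10% on n−1 df. β1 has no random term under this reading either, so a narrower point stands.

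**The illustrated error rates are not those of the SAP equation.** This is right. A reader might infer that the primary analysis as written has a 7 to 10% type I error, and the documents do not support that. A small fit with μ0i, μ3k and μ4ijk as written (10 clinics, 1,500 trials) rejected in 4.7% with no heterogeneity, 7.1% at step SD 0.01 and 13.8% at 0.02. The direction is the same, but the rates are imprecise and rest on the same assumed SDs. An SD of 0.02 equals the whole planned step. Section 4.14 reports referral numbers that were stable within clinics over time, which favours differences in level, though it says nothing about response to training.

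**μ2i and μ4ijk are not strictly redundant.** A reader might infer that they are fully confounded with the intercept and the residual. They are not: μ2i adds variance proportional to X_i², and μ4ijk adds variance only after training, growing with T². With 10 to 20 clinics they are at best weakly identifiable.

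**Section 12.6 already deals with heterogeneity.** It calls differences possible, so a reader should not infer that the plan predicts them, or that it ignores them. But its interaction test is a separate model, which the plan says is not powered, and it does not enter the primary standard error.

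**Conclusion.** The primary model is wrong as written. Its time term contradicts the prose, its interaction term contradicts its own definition, and the training effect has no clinic-level random term even if the subscripts are read charitably.

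The numerical consequence is conditional. If clinics respond alike, the error rate is nominal. Under the assumed SDs and the random-intercept simplification, it runs from about 5.5% to about 10% for step differences and falls to about 2% for slope differences alone. The direction depends on which kind of variation dominates, so the test cannot be presumed conservative. A statement that the standard errors are wrong without qualification would go beyond the documents, because they never quantify clinic differences in response.

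The point should be corrected before analysis. It is moderate in size, but it concerns the primary test and whether that test can be coded unambiguously.

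**What to change.** Rewrite the equation in 12.2 and its definitions so that they agree:

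- Include a clinic random intercept (μ0i), a clinic random training step (μ1i) attached to β1, and a clinic random time slope (μ3i).
- Index any random training-by-time term by clinic (μ4i), and keep it only if it can be estimated.
- Remove μ2i.
- If a month term shared by all clinics is also wanted, state it separately. The step would then rest on eight months, and n−1 df for clinics would no longer describe it.
- Test the training effect on clinic-level degrees of freedom (n−1). Kenward-Roger suits only a linear model with identity link and does not carry over directly to a GLMM with another link.
- Three random effects per clinic from eight observations may give singular fits. Pre-specify the fallback: a t-test on the clinic-specific step estimates.

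This is a change of SAP wording and needs no new data. The cost is somewhat wider intervals and lower power. With 10 clinics that respond alike, average power for the step falls from about 95% to about 91%. The larger losses tabulated above arise mainly if clinics respond differently.

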### 12.3 Rationale for Sample Size and Statistical Power

Sample size was established via simulation in R version 4.2.3 (R Core Team, 2023) utilizing preliminary data from clinics participating in a pilot study. This analysis is based on a within clinics, repeated measures design with two levels of EIMG exposure: Instructional Video and Onboard Training. The outcomes (e.g., referral rates) will be measured 4 times (once per month) under each level of EIMG, for a total of 8 observations per outcome per clinic. Two marginal referral rate profiles were considered in determining the sample size: a step effect of

EIMG onboarding with parallel time effect (main effects model) and a step plus accelerated time effect. A generic plot showing the two marginal rate profiles considered is presented in Figure 5.

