**Figure 5. Referral rate profiles considered in sample size analysis.**

Pilot data from 12 previously onboarded EIMG-clinics indicate the marginal referral rate (reach with eligible patients) prior to onboarding to EIMG is approximately 0.01. The following assumptions were made for both referral rate profiles. The standard deviation for the random effect of clinic, and random deviation is 0.01, the significance level for each comparison is 0.05. For the step with constant time effect, it was assumed that there was a linear change from 0.001 to 0.01 over the four months following the EIMG Instructional Video, a step-jump of 0.02, followed by a linear and parallel time effect achieving 0.04 (4%) referral rate at 8 months. For the step with accelerated time effect profile, the profile for the first 4 months was assumed to be the same as for EIMG Instructional Video with a step-jump of 0.01 followed by a linear increase to 0.04. Simulations (n=100) under each profile were conducted to compute a single empirical power, this was repeated 100 times. The power reported corresponds to the minimum empirical power observed. For a step with constant time effect a total of 10 clinics are needed to achieve a power of 92% to detect the EIMG Onboarding effect of 0.02. For the step plus accelerated time effect profile, a total of 20 clinics achieves 78% power to detect the time by EIMG status interaction when using a significance level of 0.05. Ten clinics provide 40% power to detect the step plus accelerated time effect profile.

#### 12.4 Secondary Aim 1

**To assess the effectiveness of participating in the community-based, 12-week evidence-informed PA program on EIMG-referred patient health outcomes (i.e., body weight, blood pressure, hemoglobin A1c, lipid profiles).**

*Hypothesis 1: Patients participating in the 12-week evidence-informed, community-based PA program will experience increased PA levels that is associated with a dose-response, significant reduction in body weight, systolic and diastolic blood pressure, hemoglobin A1c level, as well as improvements in their lipid profiles.*

Effectiveness is the degree to which participating in the evidence-informed PA programs improves patient physical activity levels and health outcomes (i.e., changes in cardiometabolic biometric values). Primary data for assessing effectiveness will be extracted from the Prisma

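### Section 12.2 gives the main EIMG coefficient β₁ an unqualified meaning although the model contains an EIMG-by-time term and no time origin, so β₁ is not defined as the step at onboard training

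*Combined protocol and SAP*

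**What the plan says.** Section 12.2 specifies a generalized linear mixed model for monthly clinic outcomes. Its subscripts "refer to clinic, EIMG status and time (monthly), respectively". It contains an EIMG term (β₁), a time term (β₃) and their product (β₄). The glossary says that β₁ "is the effect of EIMG" and that β₄ "is the effect of the interaction between EIMG status and time". It gives no origin for T and no coding for EIMG, leaves the link open, and names no primary contrast.

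Section 12.3 makes the comparison one within clinics, video phase against onboard-training phase, with four monthly values in each, "for a total of 8 observations per outcome per clinic". Both planning profiles begin with a "linear change from 0.001 to 0.01 over the four months following the EIMG Instructional Video". The first continues with "a step-jump of 0.02, followed by a linear and parallel time effect achieving 0.04 (4%) referral rate at 8 months". The second has a step of 0.01 and then a linear rise to 0.04. The plan reports 92% power with 10 clinics for the step, under a main effects model, and 78% with 20 clinics for the interaction.

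Month numbering varies. The section 2.0 narrative has months 1–4 and 5–8, and section 10.0 has months 2–5 and 6–9.

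**The concern.** In a model with a product term, the main coefficient is the phase difference at T = 0 and nowhere else. Effect coding of EIMG does not change that. Month indicators are not a way out: section 8.1 brings all clinics in as one wave, so month indicators would determine phase completely. T has to be numeric, and its origin decides what β₁ means.

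Under either study-month numbering, zero falls before the first observation and the training-phase line is carried back five or six months from its first point. A coefficient read as the glossary describes it would then be an extrapolation with a large standard error. It could miss a real step or carry a misleading sign in the primary analysis of at most 20 clinics.

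**Working it through.** **Inputs (section 12.3).** "The standard deviation for the random effect of clinic, and random deviation is 0.01", and "the significance level for each comparison is 0.05". I assume a two-sided test, EIMG coded 0 for video and 1 for training, an identity link (the scale of the planning profiles), and a random intercept only. The clinic effect cancels because every clinic contributes both phases. No SDs are given for the random time and interaction terms of 12.2; including them would lower power further.

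**Profiles.** Video phase: 0.001, 0.004, 0.007, 0.010 in months 1–4 (slope 0.003). Step profile, kept parallel: month 5 is 0.030 if the jump is from month 4, so the offset is 0.030 − 0.013 = 0.017. It is 0.033 if the full 0.020 is counted from the extrapolated line. Accelerated profile, main reading: 0.020 in month 5 to 0.040 in month 8 (slope 0.02/3 = 0.00667).

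**The plan's own figure.** Main effects model, 10 clinics: SE(β₁) = 0.01 × √(2.1/10) = 0.00458. For 0.017, z = 3.71 and power is Φ(3.71 − 1.96) = 0.96. The plan reports the minimum of 100 empirical powers, each from 100 runs; the expected minimum here is 0.90 (5–95% range 0.88 to 0.92). The stated 92% is therefore reproduced within two points. The 0.020 offset gives 0.99, with a minimum of 0.96.

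**Adding the interaction.** Each phase has four consecutive months, with sum of squares about the mean 1.5² + 0.5² + 0.5² + 1.5² = 5 and means 2.5 and 6.5. With T = 0 placed at month c of the 1–8 numbering,

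Var(β₁) = (0.01²/n) × [1/4 + (c − 2.5)²/5 + 1/4 + (c − 6.5)²/5].

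- c = 0: 1.5 + 8.7 = 10.2
- c = 1 (T = 0–7): 0.7 + 6.3 = 7.0
- c = −1 (T = 2–9): 2.7 + 11.5 = 14.2
- c = 5 (first post-training month): 1.5 + 0.7 = 2.2

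Power is Φ(β₁/SE − 1.96) for offsets of 0.017 to 0.020; a t reference lowers it by about 0.01.

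| Time coding | Factor | SE, 10 clinics | Step power, 10 clinics | Step power, 20 clinics | β₁, accelerated profile |
|---|---|---|---|---|---|
| T = 1–8 | 10.2 | 0.0101 | 0.39–0.51 | 0.66–0.80 | −0.0113 |
| T = 0–7 | 7.0 | 0.0084 | 0.53–0.67 | 0.82–0.92 | −0.0077 |
| T = 2–9 | 14.2 | 0.0119 | 0.30–0.39 | 0.52–0.66 | −0.0150 |
| Zero at first post-training month | 2.2 | 0.0047 | 0.95–0.99 | >0.99 | +0.0070 |

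**Accelerated profile, T = 1–8.** Training line at zero: 0.020 − 5 × 0.00667 = −0.0133. Video line at zero: 0.001 − 0.003 = −0.002. Difference: −0.0113. Yet the training months (0.020, 0.027, 0.033, 0.040) all exceed the extrapolated video line (0.013, 0.016, 0.019, 0.022).

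Other readings of this profile, still with T = 1–8:

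- Step counted from the extrapolated line (month 5 = 0.023, slope 0.00567): −0.0053 + 0.002 = −0.0033.
- Video line starting at 0.001 at activation (slope 0.00225): −0.0133 − 0.001 = −0.0143.
- The same video line with the jump placed at month 4 and slope 0.005 after it: 0 − 0.001 = −0.001.

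For β₁ = −0.0113 the chance of a significant result is 0.20 with 10 clinics and 0.35 with 20, almost all of it in the negative direction.

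**The case against.** The strongest reply is that the glossary only describes terms. Nothing in 12.2 says that β₁ alone is the primary test. Section 12.3 ties the step profile to a main effects model, where β₁ is the step, and tests the accelerated profile through β₄, which does not depend on the origin. That stands. A reader might infer that the stated 92% and 78% are wrong, and the documents do not support this: those figures concern other quantities. What is missing is any power for β₁ of the model actually written in 12.2.

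A reader might also infer that the plan will report a negative effect. That is too strong, for three reasons.

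- T = 1–8 is one reading of a monthly index. An index of 1–4 restarted within each phase gives +0.0153 under the accelerated profile, though it then mixes step and trend. With T = 0–7 the mildest reading of the profile gives a small positive value: (0.020 − 3 × 0.005) − 0.00325 = +0.0018.
- The sign needs an identity link. Least squares on the logits of the main accelerated profile gives β₁ of about +2.3 with T = 1–8; a log link gives much the same. It is still an extrapolation to month 0.
- Under the logit, centring at month 5 gives −0.25, because the video phase rises steeply on that scale (0.75 per month). The fitted month-5 log-odds are −3.62 for video and −3.62 − 0.25 = −3.86 for training, or rates of about 0.026 and 0.021. Centring alone is therefore not a cure.

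Finally, making the step profile end at exactly 0.040 from 0.030 lowers the T = 1–8 power to 0.33, but those lines are not parallel, as the plan requires. The figure should not be used.

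**Conclusion.** The concern holds as a defect of definition. The meaning given to β₁ is incorrect for the model as written under each study-month numbering in the documents, and no time origin or primary contrast elsewhere in 12.2 repairs it. On the rate scale with T = 1–8, the standard error is 2.2 times that of the main effects model (0.0101 against 0.00458), which accounts for the loss of step power at 10 clinics.

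These sizes rest on the planning profiles and SD of 12.3, a random-intercept model and the assumed coding. The fitted values of the model do not depend on the origin; what changes is the coefficient reported and tested as the EIMG effect.

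**What to change.** In section 12.2:

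1. Define T as months since onboard training, zero at the first post-training month whichever calendar numbering is kept, in both the time and the interaction terms.
2. Redefine β₁ as the phase difference at training on the link scale, and β₄ as the change in slope.
3. State the link.
4. Report the primary EIMG effect as a contrast on the referral-rate scale: the step at training, with β₄ beside it. Under a logit or log link, take the step from model-predicted rates and check that a linear time trend fits on that scale, since a poor fit in the video phase can distort or reverse the predicted step.

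The cost is a few lines of text and one extra contrast. No new data and no change of design or sample size are needed.
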